5.6.3 Other concomitant medications

Any medications, with the exceptions noted in Section 5.7 below, which are considered necessary for the patient's welfare, and which are believed will not interfere with the IP, may be given at the discretion of the investigator, providing the medications, the doses, dates, and reasons for administration are recorded in the CRF.

In addition, any unplanned diagnostic, therapeutic, or surgical procedure performed during the study period must be recorded in the comments section of the corresponding AE report.

Anticoagulant therapy: Patients with normal hepatic function who are taking warfarin may participate in this study; however, it is recommended that prothrombin time (international normalised ratio [INR] and activated partial thromboplastin time [aPTT]) be monitored carefully at least once per week for the first month, then monthly if the INR is stable. Subcutaneous heparin is permitted for those patients with normal or impaired hepatic function.

Anti-emetics/anti-diarrhoeals: Prophylactic anti-emetics and/or anti-diarrhoeals will not be routinely given. Should a patient develop nausea, vomiting, and/or diarrhoea, which, in the investigator's opinion, is considered related to the IP, then appropriate treatment may be given.

Leukopenia and/or anaemia treatment: The use of colony-stimulating factors (CSFs) (eg, granulocyte-CSF [G-CSF], or granulocyte-macrophage CSF [GM-CSF]) should be managed as deemed appropriate by the investigator for the treatment of haematological AEs during Part B of the study (see Section 5.10).

The reason(s) for use, doses, and dates of treatment should be recorded in the patient's medical records and appropriate section of the CRF.

All medications (prescriptions or over-the-counter medications) present at the start of the study or started during the study or until 30 days from the end of the last protocol treatment and different from the IP must be documented in the CRF.

5.6.4 Palliative radiotherapy

Palliative radiotherapy may be used for the treatment of pain at the site of bony metastases that were present at baseline, provided they cannot be managed with local or systemic analgesics and that the investigator does not feel that these are indicative of clinical disease progression during the study.

Study treatment should be discontinued for a minimum of 3 days before a patient undergoes therapeutic palliative radiation treatment. Study treatment should be restarted within 4 weeks as long as any bone marrow toxicity has recovered.

5.6.5 Administration of other anti-cancer agents

Patients must not receive any other concurrent anti-cancer therapy, including investigational agents, while on IP. Patients may continue the use of bisphosphonates or denosumab for bone

disease, and corticosteroids, provided the dose is stable before and during the study and they were started at least 4 weeks prior to beginning IP (see Section 4.1 and Section 4.2).

5.6.6 Live virus and bacterial vaccines

Live virus and bacterial vaccines should not be administered whilst the patient is receiving IP and during the 30-day follow-up period. An increased risk of infection by the administration of live virus and bacterial vaccines has been observed with conventional chemotherapy drugs and the effects with olaparib are unknown.

5.6.7 Medications that may NOT be administered

No other chemotherapy, immunotherapy, hormonal therapy (except hormone replacement therapy [HRT]), or other novel agent is to be permitted while the patient is receiving IP.

5.7 Treatment compliance

The administration of all medication (including IPs) should be recorded in the appropriate sections of the CRF.

For Part A, ie, when patients are at the study site, compliance will be assured by supervised administration of IP by the investigator or his/her delegate.

Patients will report any self-administered medications for the periods when they are not resident in the clinic.

For Part B, ie, when patients self-administer their olaparib, they should be given clear instructions on how and when to take their study treatment. Patients should aim to take their doses on outpatient days at similar times each day, approximately 12 hours apart. They should be instructed that the dose is to be swallowed whole with a glass of water and not chewed, crushed, dissolved or divided. It may be taken with a light meal or snack.

Patients will be issued with a Patient Diary Card, which contains clear instructions on how and when to take their study treatment, and the date of their next clinic appointment.

Study site pharmacy staff will make tablet counts at regular intervals during treatment. Compliance will be assessed by the tablet count and the information will be recorded in the appropriate section of the CRF. After the tablet count has been performed, the remaining tablets will not be returned to the patient but will be retained by the Investigative site until reconciliation is completed by the study monitor. All patients must return their bottle(s) of olaparib at the appropriate scheduled visit, when a new bottle will be dispensed. Patients will be instructed to notify study site personnel of missed doses. Dates of missed or held doses will be recorded on the CRF. Patients must return all bottles and any remaining tablets when they discontinue IP.

5.7.1 Accountability

The IP provided for this study is for use only as directed in the study protocol. It is the investigator/institution's responsibility to establish a system for handling study treatments, including IPs, so as to ensure that:

Deliveries of such products from AstraZeneca or its representative are correctly received by a responsible person

Such deliveries are recorded

Study treatments are handled and stored safely and properly as stated on the label

Study treatments are only dispensed to study patients in accordance with the protocol

The study personnel will account for all IP dispensed and returned.

At the end of the study, it must be possible to reconcile delivery records with records of usage and destroyed/returned stock. Records of usage should include the identification of the person to whom the IP was dispensed, the quantity and date of dispensing, and unused IP returned to the investigator. This record is in addition to any IP accountability information recorded on the CRF. Any discrepancies must be accounted for on the appropriate forms. Certificates of delivery and return must be signed, preferably by the investigator or a pharmacist, and copies retained in the investigator site file. Dispensing and accountability records will continue to be collected after the end of Part B for as long as patients continue to receive IP.

5.8 Discontinuation of investigational product

Patients may be discontinued from IP and assessments at any time (applies to both Parts A and B). Specific reasons for discontinuing IP are:

- Patient decision. The patient is at any time free to discontinue treatment, without prejudice to further treatment
- Adverse Event
- Severe non-compliance to study protocol
- Worsened condition
- Disease progression
- The investigator believes they are no longer deriving clinical benefit (Part B).

5.8.1 Procedures for discontinuation of a patient from investigational product

If a patient discontinues IP during Part B, then they will attend a study treatment discontinuation visit and follow the procedures described in [Table 6](#).

As described in Section 3.1, a patient may remain on study treatment after Part B if they and the investigator deem it appropriate. When the patient and the investigator decide to discontinue IP, the patient will always be asked about the reason(s) for discontinuation and the presence of any AEs. If possible, he/she will be seen and assessed by an investigator(s). Adverse events will be followed up (see Sections 6.4.3 and 6.4.4), and IP should be returned to the site pharmacy.

Any patient discontinuing IP should be seen at 30 days (± 7 days) after their last dose for the evaluations outlined in the study schedule. After discontinuation of IP, the PI/sub-investigator will perform the best possible observation(s), test(s), and evaluation(s), as well as give appropriate medication and all possible measures for the safety of the patient. In addition, they will record on the CRF the date of discontinuation, the reasons, manifestation, and treatment at the time of discontinuation. If patients discontinue IP, the AstraZeneca monitor or its representative must be informed immediately. Patients will be required to attend the treatment discontinuation visit (follow-up visit). The patient should return all IP.

After discontinuation of the IP at any point in the study, all ongoing AEs or SAEs must be followed until resolution unless, in the investigator's opinion, the condition is unlikely to resolve due to the patient's underlying disease, or the patient is lost to follow up (see Sections 6.4.3 and 6.4.4). All new AEs and SAEs occurring during the 30 calendar days after the last dose of IP must be reported (if SAEs, they must be reported to AstraZeneca or its representative within 24 hours as described in Section 6.4.4) and followed to resolution as above. Patients should be contacted at least 30 days after discontinuing IP to collect and/or complete AE information and collect IP. Any untoward event occurring subsequent to the 30-day follow-up AE reporting period that the investigator assesses as possibly related to the IP should also be reported as an AE.

If a patient is withdrawn from the study, see Section 5.9.

5.9 Withdrawal from study

Patients are at any time free to withdraw from the study (IP and assessments), without prejudice to further treatment (withdrawal of consent). Such patients will always be asked about the reason(s) and the presence of any AEs. If possible, they will be seen and assessed by an investigator. Adverse events will be followed up (see Sections 6.4.3 and 6.4.4) and questionnaires and IP should be returned by the patient.

Withdrawn patients will not be replaced.

Reasons for withdrawal from the study:

- Voluntary withdrawal by the patient who is at any time free to discontinue their participation in the study, without prejudice to further treatment
- Risk to patients as judged by the investigator and/or AstraZeneca or its representative

- Severe non-compliance to protocol as judged by the investigator and/or AstraZeneca or its representative
- Incorrectly enrolled patients, ie, the patient does not meet the required inclusion/exclusion criteria for the study
- The patient becomes pregnant
- Patient lost to follow-up.

5.10 Guidance for Investigators

The following text is guidance for investigators who treat patients with olaparib in Part B.

Where toxicity reoccurs following re-challenge with olaparib, and where further dose interruptions are considered inadequate for management of toxicity, then the patient may be considered for dose reduction or permanent discontinuation of treatment with olaparib.

Treatment may be interrupted if any CTCAE Grade 3 or 4 AE occurs that the investigator considers to be related to the administration of olaparib. Repeat dose interruptions can occur as needed for up to 2 weeks (14 days) on each occasion. If this has not resolved to at least CTCAE Grade 1 during the 2 weeks (14 days) dose interruption period, and/or the patient has already undergone a maximum of 2 dose reductions (to a minimum dose of 200 mg bd), the patient should permanently discontinue treatment with olaparib. If toxicity is appropriately resolved, then the patient should resume treatment with olaparib, but with a dose reduction according to [Table 8](#). If the event recurs with the same severity, treatment should be interrupted again and, on resolution, a further dose reduction made. If, on the re-starting treatment, the event continues to occur, the patient should permanently discontinue olaparib.

For surgery, olaparib should be stopped at least 3 days prior to planned surgery. After surgery, olaparib can be restarted when the wound has healed. No stoppage of olaparib is required for any biopsy procedure.

An exception to the management of olaparib-related toxicity is the occurrence of leukopenia and/or anaemia. In this case, the AE should be managed as deemed appropriate by the investigator (growth factor, transfusions), without interruption in IP or change in dose. However, growth factors should be discontinued once the AE has recovered to Grade 1 or better. They may be resumed, if necessary, if leukopenia/anaemia develops again and discontinued once it recovers.

The dose of olaparib must not be adjusted under any other circumstances unless the AstraZeneca Physician or representative gives prior agreement. Once the dose of olaparib has been reduced, under no account should it be re-escalated.

Olaparib should be discontinued for a minimum of 7 days before a patient undergoes therapeutic radiation treatment, or a minimum of 3 days for palliative radiation treatment (see [Section 5.6.4](#)).

All dose reductions and interruptions (including any missed doses), and the reasons for the reductions/interruptions, are to be recorded in the CRF.

Table 8 Dose reductions for olaparib in Part B only

Reduction	Dose level (tablets)
Initial dose level	300 mg bd (2 x 150 mg tablets)
1 st Dose reduction due to CTCAE Grade 3 or 4 treatment-related SAE/AEs	250 mg bd (1 x 150 mg tablet and 1 x 100 mg tablet)
2 nd Dose reduction due to CTCAE Grade 3 or 4 treatment related SAE/AEs	200 mg bd (2 x 100 mg tablets)

Management of anaemia

Adverse events of anaemia CTCAE Grade 1 or 2 (haemoglobin [Hb] ≥ 8 g/dL) should be managed as deemed appropriate by the investigator with or without interruption of study drug or change in dose. In some cases management of anaemia may require blood transfusions. However, if the patient develops anaemia CTCAE Grade 3 (Hb ≤ 8 g/dL) or higher, study treatment should be interrupted for up to maximum of 4 weeks to allow for bone marrow recovery, and the patient should be managed appropriately. Study treatment can be restarted at the same dose if Hb has recovered to ≥ 9 g/dL. Any subsequent interruptions will require study treatment dose reductions.

If a patient has been treated for anaemia with multiple blood transfusions without study treatment interruptions and becomes blood transfusion dependant as judged by the investigator, study treatment should be interrupted for up to a maximum of 4 weeks to allow for bone marrow recovery. Study treatment should be restarted at a reduced dose.

Management of prolonged haematological toxicities while on study treatment

If the patient develops prolonged haematological toxicity such as:

- ≥ 2 week interruption/delay in study treatment due to CTCAE Grade 3 or higher anaemia and/or development of blood transfusion dependence
- ≥ 2 week interruption/delay in study treatment due to CTCAE Grade 3 or higher neutropenia (ANC $< 1 \times 10^9/L$)
- ≥ 2 week interruption/delay in study treatment due to CTCAE Grade 3 or higher thrombocytopenia (platelets $< 50 \times 10^9/L$)

Weekly differential blood counts including reticulocytes (calculate reticulocyte index, RI) and peripheral blood smear should be performed. If blood parameters remain clinically abnormal after 4 weeks of dose interruption or if more than one blood cell line is affected, the patient

should be referred to a haematologist for further investigations. Bone marrow analysis or blood cytogenetic analysis should be considered at this stage according to standard haematological practice.

Development of myelodysplastic syndrome should be reported as an SAE and full reports must be provided by the Investigator to AstraZeneca Patient Safety.

Management of neutropenia and leukopenia

Adverse events of neutropenia and leukopenia should be managed as deemed appropriate by the investigator with close follow up and interruption of study drug if CTCAE Grade 3 or higher neutropenia occurs. Primary prophylaxis with G-CSF is not recommended; however, if the patient develops febrile neutropenia, study treatment should be stopped and appropriate management including G-CSF should be given according to local hospital guidelines. Please note that G-CSF should not be used within at least 24 hours of the last dose of study treatment.

Study treatment can be restarted at the same dose if an AE of neutropenia or leukopenia have been recovered up to CTCAE Grade ≤ 1 ($ANC > 1.5 \times 10^9/L$). Any subsequent interruptions will require study treatment dose reductions.

Management of thrombocytopenia

An AE of thrombocytopenia should be managed as deemed appropriate by the investigator. If a patient develops thrombocytopenia CTCAE Grade 3 or higher study treatment should be interrupted for a maximum of 4 weeks. Any subsequent interruptions will require olaparib dose reductions. In some cases, management of thrombocytopenia may require platelet transfusions. Platelet transfusions should be done according to local hospital guidelines.

Management of new or worsening pulmonary symptoms

If new or worsening pulmonary symptoms (eg, dyspnoea) or radiological abnormality occurs, an interruption in study treatment dosing is recommended and a diagnostic workup (including a high resolution computed tomography [CT] scan) should be performed, to exclude pneumonitis. Following investigation, if no evidence of abnormality is observed on CT imaging and symptoms resolve, then study treatment can be restarted if deemed appropriate by the investigator. If significant pulmonary abnormalities are identified, these need to be discussed with the AstraZeneca Study Physician.

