 - Nodules >1 cm found on ultrasound screening of a cirrhotic liver should be investigated further with either 4-phase multi-detector CT scan or dynamic contrast enhanced MRI. If the appearances are typical of HCC (ie, hyper-vascular in the arterial phase with washout in the portal venous or delayed phase), the lesion should be treated as HCC. If the findings are not characteristic or the vascular profile is not typical, a second contrast-enhanced study with the other imaging modality should be performed, or the lesion should be biopsied (level II) ([Bruix et al 2011](#)).

8. Normal organ and bone marrow function measured within 28 days prior to administration of IP as defined below:
 - Haemoglobin ≥ 9.0 g/dL, with no blood transfusions in the previous 28 days
 - Absolute neutrophil count (ANC) $\geq 1.5 \times 10^9/L$
 - White blood cells (WBC) $> 3 \times 10^9/L$
 - Platelet count $\geq 75 \times 10^9/L$
 - Serum creatinine ≤ 1.5 x institutional ULN
9. Calculated serum creatinine clearance > 50 mL/min (using Cockcroft-Gault formula or by 24-hour urine collection)
10. Eastern Cooperative Oncology Group (ECOG) performance status ≤ 2 .
11. Patients must have a life expectancy ≥ 8 weeks.
12. Evidence of non childbearing status for women of childbearing potential, or postmenopausal status: negative urine or serum pregnancy test within 28 days of study treatment, confirmed prior to treatment on Day 1 of the first treatment period in Part A

Postmenopausal is defined as:
 - Amenorrheic for 1 year or more following cessation of exogenous hormonal treatments
 - Luteinising hormone and follicle-stimulating hormone levels in the postmenopausal range for women under 50 years of age
 - Radiation-induced oophorectomy with last menses > 1 year ago
 - Chemotherapy-induced menopause with > 1 year interval since last menses
 - Surgical sterilisation (bilateral oophorectomy or hysterectomy).
13. Patients are willing and able to comply with the protocol for the duration of the study including undergoing treatment and scheduled visits and examinations.
14. Patients must be on a stable concomitant medication regimen (with the exception of electrolyte supplements), defined as no changes in medication or in dose within 2 weeks prior to start of olaparib dosing, except for bisphosphonates, denosumab and corticosteroids, which should be stable for at least 4 weeks prior to start of olaparib dosing.

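### Section 5.10 tells investigators both to continue and to interrupt olaparib for drug-related Grade 3 or higher anaemia in Part B, and nothing says which instruction governs

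*Protocol*

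**What the plan says.** All of the text at issue is in Protocol Section 5.10, which is introduced as guidance for Part B.

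- **General rule.** Treatment may be interrupted for Grade 3 or 4 events judged related to olaparib: "Repeat dose interruptions can occur as needed for up to 2 weeks (14 days) on each occasion". After recovery, treatment resumes at a reduced dose from Table 8.
- **Exception.** "An exception to the management of olaparib-related toxicity is the occurrence of leukopenia and/or anaemia". Such events are to be "managed as deemed appropriate by the investigator (growth factor, transfusions), without interruption in IP or change in dose". Two further sentences say when growth factors stop and when they may be resumed.
- **Management of anaemia.** At Grade 1 or 2 the investigator may or may not interrupt or change the dose. At Grade 3 or higher, "study treatment should be interrupted for up to maximum of 4 weeks to allow for bone marrow recovery". The same dose may be restarted once Hb is at least 9 g/dL. After that, "Any subsequent interruptions will require study treatment dose reductions".
- **Prolonged haematological toxicities.** The triggers for weekly blood counts include a "2 week interruption/delay in study treatment due to CTCAE Grade 3 or higher anaemia and/or development of blood transfusion dependence"; the text puts a ≥ sign before the figure.
- **Management of neutropenia and leukopenia.** The text calls for "interruption of study drug if CTCAE Grade 3 or higher neutropenia occurs" and gives a restart rule for both neutropenia and leukopenia.

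**The concern.** An investigator who reads the exception literally keeps a patient with Grade 3 or 4 anaemia on an unchanged dose and treats with transfusion or growth factor. One who reads the anaemia subsection stops the drug. The choice concerns a toxicity that the protocol itself foresees. Section 1.1.2 names bone marrow as the primary target organ in animals, with recovery once olaparib is withdrawn, and Section 1.1.3.1 lists anaemia, at low grade, among the most common adverse events.

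Patient safety in Part B is at stake first. The Part B tolerability data come second: safety and tolerability of multiple doses belong to the secondary objective (Section 2.2), and interruptions and reductions are recorded in the CRF. If sites read the section differently, those records would partly reflect the reading and not only the drug.

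**Working it through.** The protocol has no figure to reproduce, so the check is a comparison of texts with a little arithmetic on their limits.

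**Step 1. Does the exception reach Grade 3 or higher?** It states no grade limit. The rule it departs from is the one for related Grade 3 or 4 events, so those grades are what it chiefly exempts.

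**Step 2. The instructions side by side, for olaparib-related events in Part B.**

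| Event | Exception paragraph | Toxicity-specific subsection |
|---|---|---|
| Anaemia, Grade 1 or 2 | No interruption, no dose change | Interruption or dose change allowed |
| Anaemia, Grade 3 or higher | No interruption, no dose change | Interrupt, at most 4 weeks; dose reduction at later interruptions |
| Leukopenia with Grade 3 or higher neutropenia | No interruption, no dose change (for the leukopenia) | Interrupt (for the neutropenia) |

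The second row is a direct contradiction. In the first row one text permits what the other rules out. The third is a lesser conflict, because the exception does not name neutropenia and the clash arises only when the two occur together.

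**Step 3. Is there a ranking sentence?** The contrast drawn in the anaemia subsection is between Grade 3 or higher and Grade 1 or 2 within that subsection; it does not refer back to the exception. Section 5.6.3 leaves growth factor use to the investigator and points to Section 5.10. Section 5.8 lists an adverse event as a reason for stopping the drug but ranks nothing. The sentence in Section 5.10 that bars other dose adjustments without the sponsor's agreement does not rank the two texts either.

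**Step 4. Which rule is intended?** The prolonged-toxicity list takes for granted that treatment has been interrupted for Grade 3 or higher anaemia. That could not happen under the exception, so the subsections are the intended rule.

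**Step 5. Size for one patient.** Exception: 0 days off drug. Subsection: at most 4 × 7 = 28 days, or 28 × 2 = 56 scheduled twice-daily doses. These are maxima, not expected values.

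**Step 6. Distance from entry to the trigger.** Inclusion criterion 8 requires "Haemoglobin ≥ 9.0 g/dL, with no blood transfusions in the previous 28 days", and Section 3.1 applies the entry criteria to the Part B baseline. The smallest margin is 9.0 − 8.0 = 1.0 g/dL.

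**Step 7. Grade bands.** The anaemia subsection gives Grade 1 or 2 as Hb ≥ 8 g/dL and Grade 3 as Hb ≤ 8 g/dL. The value 8.0 g/dL lies in both. With Hb < 8 g/dL for Grade 3 it lies in one.

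**The case against.** The best defence is that a careful reader would reach the right answer. The anaemia subsection has its own title, a threshold, a maximum duration and a restart rule, and the next subsection assumes interruption. The section is called guidance, and Sections 5.8 and 5.9 allow stopping for an adverse event or for risk to the patient in any case. The overlap at 8 g/dL is a single value, and Section 6.4.3 already fixes CTCAE v4.0 as the grading scale.

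Much of this stands. It shows what was meant, and it makes the grade overlap a minor matter. It does not remove the contradiction: the exception also names anaemia specifically, and this is the protocol's dose-management text for haematological toxicity in Part B.

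Four stronger readings go further than the document allows.

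- A reader might infer that the conflict covers every Grade 3 or higher anaemia. The exception concerns olaparib-related toxicity, while the subsection covers anaemia of any cause, so the direct clash is limited to cases judged related.
- A reader might count the rule on transfusion dependence as a further contradiction. It describes what to do after a patient has been transfused without interruption, so it follows on from that route.
- A reader might carry the 14-day limit of the general rule over to neutropenia, because that subsection states no maximum. The prolonged-toxicity list provides for neutropenia interruptions of 2 weeks or more, with haematologist referral if counts are still abnormal after 4 weeks. A 14-day limit would cut across that pathway.
- A reader might take the 1.0 g/dL margin as a measure of risk. It is the lowest permitted entry value, and the protocol gives no rate of Grade 3 or higher anaemia.

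**Conclusion.** The contradiction is real and should be fixed. For olaparib-related anaemia in Part B, the exception and the anaemia subsection cannot both be followed at Grade 3 or higher, and they also disagree on what is allowed at Grade 1 or 2. Leukopenia with Grade 3 or higher neutropenia meets a lesser form of the same problem.

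For an affected patient the difference is between no interruption and one of up to 28 days, plus dose reduction at any later interruption. How many patients this would concern is unknown. The consequence is confined to Part B safety management and tolerability data; Part A uses a single dose and its pharmacokinetic analysis is unaffected.

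The conclusion rests on reading the exception as covering all grades, which follows from its missing grade limit and from the Grade 3 or 4 rule it departs from.

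**What to change.** Make one of two changes to the exception paragraph in Section 5.10, and in either case keep its sentences on stopping and resuming growth factors.

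1. Add: *For anaemia, neutropenia and leukopenia, the toxicity-specific subsections below take precedence over this paragraph for interruption, restart and dose.*
2. Or delete the clause that rules out interruption and dose change.

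The first is preferable because it also settles restart and dose, and it covers Grade 1 or 2 anaemia and leukopenia in the same sentence. Add no 14-day limit for neutropenia; if a maximum is wanted there, it is a clinical decision for the sponsor.

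As a minor correction, define Grade 3 anaemia in the anaemia subsection as Hb < 8 g/dL.

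The cost is a short text change with notice to sites. Because it touches safety dosing rules, it may need a protocol amendment with ethics committee and, where applicable, regulatory approval under Section 8.5. It needs no new data and no additional patients.

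### Section 5.10 both rules out and requires interruption and dose reduction for severe anaemia in Part B, and nothing says which text prevails

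*Protocol*

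**What the plan says.** Section 5.10 opens with a general scheme for Grade 3 or 4 events that the investigator attributes to olaparib. Treatment may be interrupted: "Repeat dose interruptions can occur as needed for up to 2 weeks (14 days) on each occasion". If the event has not come down to Grade 1 within those 14 days, the patient stops olaparib for good. If it has resolved, the patient "should resume treatment with olaparib, but with a dose reduction according to" Table 8.

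The same opening text then carves out two events: "An exception to the management of olaparib-related toxicity is the occurrence of leukopenia and/or anaemia". These are left to the investigator's judgement ("growth factor, transfusions), without interruption in IP or change in dose"). The carve-out has no grade limit and does not refer to the sub-headings that follow. The next paragraph forbids any other dose adjustment without prior agreement from the sponsor's physician or representative.

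The event-specific text under the later sub-headings reads differently:

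- **Anaemia, Grade 1 or 2:** it "should be managed as deemed appropriate by the investigator with or without interruption of study drug or change in dose".
- **Anaemia, Grade 3 or higher:** "study treatment should be interrupted for up to maximum of 4 weeks to allow for bone marrow recovery". Then, "Study treatment can be restarted at the same dose if Hb has recovered to" at least 9 g/dL. Later interruptions require dose reductions.
- **Transfusion-dependent anaemia:** interruption for up to 4 weeks, then restart at a reduced dose.
- **Neutropenia and leukopenia:** investigator's judgement, with "interruption of study drug if CTCAE Grade 3 or higher neutropenia occurs" and treatment stopped for febrile neutropenia. Restart at the same dose is allowed once neutropenia or leukopenia has recovered; later interruptions require dose reductions.
- **Thrombocytopenia, Grade 3 or higher:** interruption for at most 4 weeks.

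**The concern.** An investigator with a Grade 3 anaemia patient in Part B finds two instructions in the same section. One keeps olaparib going at an unchanged dose; the other stops it for up to 4 weeks and may lead to a lower dose. Both name anaemia explicitly.

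The first matter at stake is patient safety. Section 1.1.2 names bone marrow as the primary target organ of toxicity, and Section 1.1.3.1 lists low-grade anaemia among the most common adverse events. Inclusion criterion 8 admits patients with haemoglobin from 9.0 g/dL, which is 1 g/dL above the threshold at which the two texts part.

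The second is the data. The secondary objective is safety and tolerability of single and multiple doses in patients with and without hepatic impairment. About 30 patients at about 20 sites is 30/20 = 1.5 patients per site, so a site's reading of Section 5.10 cannot be separated statistically from the characteristics of the one or two patients it treats.

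**Working it through.** The protocol states no figure on this point and none has to be recomputed. The check is to set the opening paragraphs of Section 5.10 against the event-specific text and ask, event by event, whether one course of action satisfies both.

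| Event | Opening paragraphs | Event-specific text | Can both be followed? |
|---|---|---|---|
| Anaemia, Grade 1–2 | No interruption, no dose change | Either is allowed | Yes, by not interrupting and not changing dose |
| Anaemia, Grade 3 or higher | No interruption | Interrupt, up to 4 weeks | **No** |
| Anaemia, later interruptions | No dose change | Dose reduction required | **No** |
| Anaemia, transfusion-dependent | No interruption, no dose change | Interrupt, restart at reduced dose | **No** |
| Leukopenia with Grade 3 or higher neutropenia | No interruption for leukopenia | Interrupt for the neutropenia; restart criterion names leukopenia | **No** |
| Leukopenia without such neutropenia | No interruption | No explicit trigger; the restart sentence implies an interruption | Unclear |
| Thrombocytopenia, Grade 3 or higher | Permanent stop if not Grade 1 by day 14 | Interrupt for at most 4 weeks | **No**, if unresolved after day 14 |
| Neutropenia, Grade 3 or higher, first restart | Resume at a reduced dose | May restart at the same dose | **Not if** the same-dose option is used |

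Three points on reading the table.

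1. The anaemia rows are the core. The conflict does not depend on inference: the opening text excludes interruption and dose change for anaemia at every grade, and the later text directs both in defined circumstances.

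2. The thrombocytopenia and neutropenia rows arise because neither event is named in the carve-out, so the general scheme applies to them. For thrombocytopenia the gap is 28 − 14 = 14 days. In that window one text has ended treatment permanently and the other still counts the patient as interrupted. The text on prolonged haematological toxicity also provides for interruptions of 2 weeks or more and for reassessment after 4 weeks, which fits poorly with a permanent stop at day 14.

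3. Haemoglobin boundary: as printed, the Grade 1–2 band is 8 g/dL or above and the Grade 3 band is 8 g/dL or below. A value of exactly 8 g/dL satisfies both, and the two bands carry different instructions.

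**The case against.** The best defence is that Section 5.10 is guidance, that its general rule is permissive about starting an interruption, and that a general paragraph followed by event-specific sub-headings is ordinarily read as specific over general. That reading has some force for thrombocytopenia and neutropenia, which makes those conflicts weaker. It does not settle anaemia, because the carve-out is itself event-specific: it names anaemia and leukopenia. No sentence in the section says that the sub-headings prevail.

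Several stronger readings are tempting, and the protocol does not support them.

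- A reader might infer three routes for Grade 3 anaemia, adding the 14-day limit and permanent stop. The carve-out removes anaemia from the general scheme, so there are two routes. For the same reason, the duration and restart-dose conflicts with the general scheme hold for thrombocytopenia and neutropenia respectively, not for anaemia.
- A reader might infer that all leukopenia is affected, or that dose reduction is required from the first interruption. The written trigger is Grade 3 or higher, or febrile, neutropenia. After a first interruption the same dose is allowed, except in transfusion dependence.
- A reader might put the effect at 10 to 20 percentage points on a group's discontinuation rate. That is only 1/10 and 2/10. It assumes ten Part B patients per group, although entry to Part B is optional, and no event rate stands behind one or two affected patients.
- A reader might call the Part B data uninterpretable. Section 5.10 requires every interruption and reduction to be recorded with its reason, so differing practice would be visible, and Section 12.2.3 plans descriptive summaries only.

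The haemoglobin overlap is also minor. Section 6.4.3 makes CTCAE v4.0 the grading reference, which could settle the grade, and a comparison sign may have been misread when the text was extracted from PDF.

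**Conclusion.** The contradiction is real and needs correcting. It is direct and certain for Grade 3 or higher anaemia and for transfusion-dependent anaemia. It is real but secondary for leukopenia accompanied by Grade 3 or higher neutropenia, for thrombocytopenia unresolved after 14 days, and for the restart dose after neutropenia. It is marginal for haemoglobin of exactly 8 g/dL, where it assumes that the printed signs are correct.

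The consequence is that sites may manage the same toxicity differently. That is a patient-safety risk, and it is an avoidable source of site-dependent variation in interruptions, reductions and discontinuations when Part B safety is described by hepatic group. The size cannot be quantified: the protocol gives low-grade anaemia as common but no frequency for Grade 3 or higher or transfusion-dependent anaemia. The primary analysis is unaffected, because Part A is a single dose and Section 5.10 applies to Part B only.

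**What to change.** The sponsor's medical team should reconcile the opening paragraphs of Section 5.10 with its sub-headings on anaemia, prolonged haematological toxicity, neutropenia and leukopenia, and thrombocytopenia. The result should be one consistent set of instructions for when to interrupt, for how long at most, at what dose to restart, and on which side of the boundary a haemoglobin of exactly 8 g/dL falls. Superseded text should be removed, and a sentence should state which text takes precedence if a general and an event-specific instruction differ. Which clinical rule is right is for the medical team; none is proposed here.

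The cost is a protocol text amendment, with the approvals that Section 8.5 requires, and a letter to sites. Design, sample size and the planned analyses do not change.
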